## 4 SELECTION AND WITHDRAWAL OF PARTICIPANTS

Participants who meet all inclusion criteria and none of the exclusion criteria will be eligible to participate in the study.

Individuals who do not meet the criteria for participation in this study (screen failure) or individuals who have not completed the screening assessments within the specified time period may be rescreened, after discussion with the Sponsor. Rescreened participants will be assigned a new participant number. Those tests that require repetition will be repeated, as needed, upon the agreement of the Sponsor.

### 4.1 INCLUSION CRITERIA

1. Male or female
2. Age 25 to 85 years, inclusive.
3. Must sign an informed consent form (ICF) (or their legally acceptable representative must sign) indicating that he or she understands the purpose of, and procedures required for the study and is willing to participate in the study and consider participation in the long-term follow-up study.
4. Diagnosis of probable idiopathic Parkinson's disease by United Kingdom Parkinson's Disease Society Brain Bank criteria and no evidence of another Parkinsonian disorder.
5. Completed cranial MRI and FDG-PET during Screening. MRI and FDG-PET scans obtained during Screening will be used as baseline tests and will be reviewed to verify the diagnosis of Parkinson's disease.
6. Presence of typical features of Parkinson's disease and history of levodopa responsiveness demonstrated for at least 12 months prior to Screening.
7. Progressive Parkinsonian disability with demonstrated response from continued use of levodopa (or from other Parkinson's disease medications if part of the treatment regimen), but with insufficient response to medication (e.g., uncontrolled tremors, increased off-time, decreased on-time, motor fluctuations, dyskinesias, gait disturbance) or with intolerable side effects as judged by the Investigator.
8. Severe disability, which includes a practically defined "off" state MDS-UPDRS Part 3 (motor examination) score of  $\geq 25$  points after overnight omission of all Parkinson's disease medications.
9. Continued use of an unchanged stable anti-Parkinsonian drug regimen for  $\geq 4$  weeks prior to Screening.
10. Willingness to not add any new treatments for Parkinson's disease for the duration of the 6-month study period. Adjustments in the dose of dopaminergic medications are permitted when medically indicated.
11. Agrees not to participate in another interventional study until completion of this study and the long-term follow-up study.

12. Willingness to not receive DBS or any other approved or experimental surgical therapy for PD during the 6-month study period.
13. Receiving stable doses of other medications for any other underlying medical conditions for  $\geq 4$  weeks prior to Screening.
14. Must demonstrate a full understanding of the Hauser Patient Diary rating criteria and demonstrate proficiency in completing the diary by reaching at least 66% of diary concordance with a site rater.
15. A woman must be:
  - a. Not of childbearing potential or:
  - b. Of childbearing potential and
    - Practicing a highly effective method of contraception (failure rate of  $<1\%$  per year when used consistently and correctly) and agrees to remain on a highly effective method for at least 6 months after receiving the last dose of study intervention. The Investigator should evaluate the potential for contraceptive method failure (e.g., noncompliance, recently initiated) in relationship to the first dose of study intervention. Examples of highly effective methods of contraception are hormonal or barrier methods of contraceptive, or sexual abstinence.

NOTE: Participants who are randomly assigned to sham surgery will also be required to adhere to this restriction to receive treatment in Study MGT-GAD-026.

16. If male, willing to use barrier and spermicide form of contraception or maintain sexual abstinence for at least 6 months following surgery.

NOTE: Participants who are randomly assigned to sham surgery will also be required to adhere to this restriction to receive treatment in Study MGT-GAD-026.

17. Ability to discontinue use of aspirin, other antiplatelet drugs, or anti-coagulants at least 1 week prior to surgery and for 1 week following surgery.

#### **4.2 EXCLUSION CRITERIA**

1. Women who are pregnant or breastfeeding. Women of childbearing potential are required to have a negative serum pregnancy test at the Screening Visit and within approximately 1 week prior to surgery on Day 1. Participants are considered not of childbearing potential if they are surgically sterile (i.e., they have undergone a hysterectomy or bilateral oophorectomy), or are postmenopausal.
2. Any experimental therapy (drug or biologic) within 3 months prior to Screening.
3. Have a known allergy to any of the non-investigational drugs (e.g., antibiotics and local anesthesia) to be used in the study.
4. Known allergies, hypersensitivity, or intolerance to AAV-GAD excipients.
5. Any prior history of brain surgery for Parkinson's disease.
6. Ongoing treatment with dopamine receptor-blocking drugs.

7. History of any serious cerebral insult, such as head injury, or central nervous system infection, or uncontrolled seizures.
8. Mental retardation or impaired cognitive abilities, as judged by patient history or cognitive impairment as defined by Montreal Cognitive Assessment (MoCA)  $\leq 20$ .
9. Focal or lateralized central nervous system (CNS) neurological deficits other than mild memory disturbance.
10. Neurological features suggestive of the diagnosis of a “Parkinson-plus” disorder (such as progressive supranuclear palsy, multiple system atrophy, corticobasal ganglionic degeneration, or “lower body” Parkinsonism) or normal pressure hydrocephalus.
11. Evidence of lesions or other significant abnormalities on cranial neuroimaging (either CT, MRI, or  $^{18}\text{FDG-PET}$ ) suggesting findings compatible with a probable diagnosis other than Parkinson's disease.
12. Alanine aminotransferase and/or aspartate aminotransferase  $>1.5$  upper limit of normal (ULN) or alkaline phosphatase  $>1.5$  ULN.
13. Clinically relevant abnormality on 12-lead ECG.
14. Administration of any live virus vaccine within 4 weeks of surgery.
15. Evidence of other significant medical or psychiatric disorders, such as psychosis, frequent occurrence of hallucinations, severe depression, significant cognitive decline in recent months, systemic organ failure, or bleeding diathesis, not attributable to adverse effects of anti-Parkinsonian medications.
16. Evidence of active impulse control disorder, or substance or alcohol abuse unrelated to use of dopaminergic medication.
17. Significant concurrent or recently diagnosed ( $\leq 2$  months prior to the Screening Visit) medical condition that, in the opinion of the Investigator, could affect the participant's ability to tolerate or complete the study.
18. Current immunosuppressive therapy or underlying disorder associated with diminished immunocompetence.
19. Serum platelet count of  $<80,000/\text{mm}^3$ , international normalized ratio (INR)  $>1.3$ , or partial thromboplastin time (PTT)  $>40$  seconds.
20. Score of  $\geq 20$  on the Beck Depression Inventory-II.
21. Acute or chronic systemic and/or local skin infections involving the scalp.
22. Criterion removed in protocol version 6.0.
23. Has any other condition that, at the consideration of the Investigator, makes them inappropriate for entry into the study.
24. Is an employee of MeiraGTx.
25. Is an employee of the Investigator or study site, with direct involvement in the proposed study or other studies under the direction of that Investigator or study site, as well as family members of the employees or the Investigator.

#### **4.3 WITHDRAWAL CRITERIA**

Participation in this clinical study may be discontinued for any of the following reasons:

- The participant withdraws consent or requests discontinuation from the study for any reason
- Occurrence of any medical condition or circumstance that exposes the participant to substantial risk and/or does not allow the participant to adhere to the requirements of the protocol
- Any SAE, clinically significant AE, severe laboratory abnormality, intercurrent illness, or other medical condition that indicates to the Investigator that continued participation is not in the best interest of the participant
- Requirement of prohibited concomitant medication
- Participant failure to comply with protocol requirements or study-related procedures
- Termination of the study by the sponsor or the regulatory authority

The reason for participant withdrawal must be documented in the electronic case report form (eCRF).

Participants who withdraw prior to surgery will be replaced. Participants who withdraw after surgery will not be replaced.

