#### *Emergency unblinding procedure*

Code-breaking and unblinding in the event of medical emergencies can be done by the Investigator via physical code break envelopes stored at the site in accordance with the site's blinding/unblinding procedures.

Unblinding by the Investigator should occur only in the event of an AE/SAE for which it is necessary to know the treatment assignment to determine an appropriate course of therapy for the participant. The Investigator should first discuss options with the Sponsor, if possible, with due consideration of the safety of the participant.

Participants for whom the code has been broken by the Investigator will be encouraged to attend all post-treatment visits as indicated in the Schedule of Activities. Code breaking will be documented in the eCRF.

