## **5.6 PRIOR AND CONCOMITANT MEDICATIONS AND/OR PROCEDURES**

### **5.6.1 Excluded Medications and/or Procedures**

The following medications and procedures will be prohibited:

- Deep brain stimulation
- Other brain surgery for Parkinson's disease
- Other experimental therapy (drug or biologic) within 3 months prior to Screening and throughout participation in the study
- Dopamine receptor-blocking drugs
- Live virus vaccine within 4 weeks of surgery
- Immunosuppressive therapy
- New treatment for Parkinson's disease.

Note: Adjustments in the dose of dopaminergic medications are allowed when medically indicated.

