## **8.2.6 Safety Reporting Requirements**

All AEs, serious and non-serious, will be fully documented on the appropriate eCRF. For each AE, the Investigator must provide its duration (start and end dates or ongoing), severity, assessment of causality, and whether specific action or therapy was required.

All adverse events and special reporting situations, whether serious or non-serious, will be reported from the time a signed and dated ICF is obtained until the participant's last study visit.

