### **8.2.6.2 Serious Adverse Event Reporting – Procedures for Investigators**

All adverse events are to be recorded in the participant's medical notes and the CRF from the date of written informed consent until the last study visit. The Sponsor or designee must be notified of all SAEs within 24 hours of the Investigator becoming aware of the event during this period. The Investigator will respond to any SAE queries raised by the Sponsor or designee as soon as possible.

After the last visit, any SAE reported to the Investigator and considered causally related to study treatment should be reported as part of the follow-up study.

The SAE form must be completed by the Investigator (i.e., the individual named on the delegation of responsibilities list who is responsible for the participant's care) with attention paid to the severity, and causality of the event. In the absence of the Investigator, the SAE form should be completed and signed by a member of the site study team and emailed as appropriate within the required timeframe. The Investigator should check the SAE form at the earliest opportunity, make any changes necessary, sign and then email to the Sponsor or designee (see Section 8.2.8). Systems will be in place at the site to enable the Investigator to check the form for clinical accuracy as soon as possible.

The minimum components required for reporting a SAE are the patient ID and year of birth, name of reporting Investigator and sufficient information on the event to confirm seriousness. Any further information regarding the event that is unavailable at the time of the first report should be sent as soon as it becomes available.

For information on code-breaking and unblinding in the event of medical emergencies, please refer to Section 5.4.

Participants must be followed up until clinical recovery is complete and laboratory results have returned to normal or baseline values, or until the event has stabilized. Follow-up should continue after completion of the study if necessary. Follow-up SAE forms (clearly marked as follow-up) should be completed and emailed to the Sponsor or designee (see Section 8.2.8) as further information becomes available. Additional information and/or copies of test results, etc. may be provided separately. The participant's name and full date of birth must not be used in any correspondence and must be blacked out and replaced with study identifiers on any test results, should they be provided.

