### 8.2.6.3 Pregnancy Reporting

If a participant becomes pregnant prior to receiving treatment, the participant should not receive treatment and will be replaced. If a participant becomes pregnant after receiving treatment, the participant will continue the protocol-defined assessments. However, any assessment that in the opinion of the Investigator or primary physician would be deemed a risk to the pregnancy may be omitted or deferred.

In case a pregnancy occurs after study treatment is administered, the participant's general practitioner is to be notified that she is participating in a gene therapy study and that, although the risks involved are minimal, there is a chance of gene transfer to the unborn child.

A pregnancy is not considered to be an AE or SAE; however, it must be reported to the Sponsor or designee using a pregnancy report form, within 24 hours of the Investigator becoming aware of the event.

If the female partner of a male participant becomes pregnant while the participant is receiving study drug or within the safety follow-up period defined in the protocol, the Investigator should notify the Sponsor or designee as described above.

After written informed consent is obtained from the female partner (via a pregnant partner consent form), the pregnancy should be followed until its outcome is known. Once the outcome of the pregnancy is known, the pregnancy report form should be completed and faxed/mailed to the Sponsor or designee (see Section 8.2.8). If the outcome of the pregnancy meets the criteria for immediate classification as an SAE (i.e., postpartum complication, spontaneous abortion, stillbirth, neonatal death, or congenital anomaly), the Investigator should follow the procedures for reporting an SAE.

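### After the one-time infusion, section 4.3 still lets participation end for an adverse event or prohibited medication, and full AE collection then stops short of Week 26

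*Combined protocol and SAP*

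**What the plan says.** All references are to the protocol.

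- **Grounds for ending participation (4.3).** The list is permissive: participation may be discontinued. One ground is "Any SAE, clinically significant AE, severe laboratory abnormality, intercurrent illness, or other medical condition that indicates to the Investigator" that staying in the study no longer serves the participant. Another, with no such judgment attached, is "Requirement of prohibited concomitant medication". Neither distinguishes a participant awaiting surgery from one already infused. Section 4.3 adds: "Participants who withdraw after surgery will not be replaced".
- **What is prohibited (5.6.1).** The list covers medications and procedures together. It includes "Immunosuppressive therapy", newly added treatment for Parkinson's disease, and deep brain stimulation (DBS).
- **AE window (8.2.6).** AEs, serious or not, "will be reported from the time a signed and dated ICF is obtained until the participant's last study visit". Table 1 pairs the Week 26 visit with early withdrawal (EW), so the EW visit is the last visit for someone who leaves.
- **After the last visit (8.2.6.2).** The rule is that "any SAE reported to the Investigator and considered causally related to study treatment should be reported as part of the follow-up study". Events already open are followed until they resolve or stabilise.
- **Two neighbouring situations.** Section 8.2.6.3 says: "If a participant becomes pregnant after receiving treatment, the participant will continue the protocol-defined assessments". Assessments that would endanger the pregnancy may be left out or postponed. Under 5.4, participants whose code has been broken "will be encouraged to attend all post-treatment visits as indicated in the Schedule of Activities".

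**The concern.** In a trial with repeated dosing, an adverse event or a forbidden rescue drug can be a reason to stop treatment. Here the treatment is a single infusion that cannot be withdrawn. Once surgery is over, the two grounds in 4.3 can relieve the participant of visit burden, but they cannot reduce exposure. The statistical consequence is loss of observation.

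That loss is tied to the outcome being measured. Safety and tolerability is the primary objective, and immune response is one of the listed safety measures (8.7). A participant who needs immunosuppression for a reaction meets a stated ground for leaving the study that exists to detect such reactions. A participant given a new Parkinson's drug for worsening disease meets it too.

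Missing time can only lower the number of events counted, and events never collected cannot be restored by an analysis rule. With five participants per dose arm, four in sham and no replacement after surgery, one such exit is visible in every AE table.

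**Working it through.** The plan states no dropout rate and no figure on this point, so there is nothing to reproduce. The check has two parts.

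**1. What is still required between an EW visit and Week 26**

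| Item | Rule | Required to Week 26 after an exit? |
|---|---|---|
| SAE judged related | 8.2.6.2 | Yes, through the follow-up study |
| SAE already open | 8.2.6.2 | Yes, until resolved or stable |
| MRI, Parkinson's and other neurological features | 6.3 | Encouraged only |
| New SAE judged unrelated | 8.2.6 | No |
| New non-serious AE outside neurology | 8.2.6 | No |
| Scheduled laboratory, vital-sign and antibody assessments | Table 1, 6.3 | No; one EW panel stands in for them |

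Section 4.4 says AAV-GAD recipients will be followed long term. Section 3.1 describes entry to that study as an invitation on completing this one, and no route is stated for someone who leaves early.

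**2. Size of one exit**

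Inputs: 5 participants per dose arm and 4 in sham (5.3), so 10 in the pooled active arms; 26 weeks of follow-up; Day 29 taken as Week 4 (28 days after Day 1).

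Full follow-up in person-weeks: 5 × 26 = 130 (dose arm), 10 × 26 = 260 (pooled active), 4 × 26 = 104 (sham).

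Weeks of full AE collection lost = 26 − week of exit:

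| Exit | Weeks lost | Share of that participant's 26 weeks | Dose arm | Pooled active | Sham |
|---|---|---|---|---|---|
| Day 29 | 26 − 4 = 22 | 22/26 = 84.6% | 22/130 = 16.9% | 22/260 = 8.5% | 22/104 = 21.2% |
| Week 12 | 26 − 12 = 14 | 14/26 = 53.8% | 14/130 = 10.8% | 14/260 = 5.4% | 14/104 = 13.5% |

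These are ceilings, because the first three rows of the first table may still yield data. After an exit at Day 29, the scheduled contacts at Weeks 12, 19 and 26 give way to one EW panel.

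One first AE of a given type that goes unseen changes the percentage with that AE by 1/5 = 20 points in a dose arm, 1/10 = 10 pooled, or 1/4 = 25 in sham.

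The documents do not say how often a site would end participation on these grounds, so the expected loss cannot be calculated.

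**The case against.** The strongest reply is that 4.3 is permissive, that its AE ground requires a judgment about the participant's interest, and that an ill participant may have good reason to be spared later visits. Those visits involve at least 12 hours without dopaminergic medication and, at Week 26, FDG-PET and MRI. All of this stands. It argues for letting individual assessments be dropped, which 8.2.6.3 already allows in pregnancy. It does not argue for ending AE collection, which a telephone call can continue.

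Five stronger readings are tempting, and the documents do not support them:

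- *That safety capture ends altogether at the EW visit.* It does not. Related SAEs, open events, 6.3 and 4.4 all remain.
- *That any SAE is a ground for exit, so earlier SAE rates show how often it would apply.* SAEs occurred in 3 of 12 Phase 1 participants and 1 of 22 AAV-GAD participants in the blinded part of Phase 2 (1.4.2). They were reported as unrelated and resolved. None is described as leading to withdrawal or to a judgment that the participant should leave.
- *That the protocol contradicts itself.* Section 5.4 only encourages attendance, and neither code-breaking nor pregnancy is a 4.3 ground. These sections show a different approach to neighbouring cases, not a conflict.
- *That rescue by DBS triggers exit.* Section 4.3 says medication, and 5.6.1 lists medications and procedures together. Extending the ground to DBS is an inference. Immunosuppression and new Parkinson's drugs need none.
- *That the bias must favour AAV-GAD.* In Phase 2, worsening Parkinsonism was reported as an AE in 8 sham participants, with none listed for AAV-GAD (1.4.2). If such worsening led to a prohibited new drug, the exits would fall in sham and make sham look safer.

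The long-term study's own protocol (MGT-GAD-026) is not among the documents and may say how early leavers enter it.

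**Conclusion.** The concern holds in a limited form. Following the rules as written, a participant can be taken out of full safety observation after an irreversible infusion because of an adverse event or its treatment. The resulting gap is specific: new non-serious AEs outside neurology, SAEs judged unrelated, and the scheduled laboratory, vital-sign and antibody assessments up to Week 26.

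The loss is outcome-dependent and lowers AE counts in whichever arm it occurs, so the direction of bias between arms cannot be stated in advance. Its frequency is unknown and may be zero; the size of a single exit is as calculated above.

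The conclusion assumes that the EW panel is done when the participant leaves, as the combined Week 26/EW column implies, and that this visit closes the AE window. It is a cheap improvement to study conduct, not a flaw that undermines the design.

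**What to change.** Add to 4.3:

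> *After surgery, the need for a prohibited medication or procedure, or an AE/SAE, is recorded but is not by itself a reason to end participation. AE reporting and scheduled safety assessments continue to Week 26 unless consent is withdrawn; any assessment the Investigator considers a risk or not in the participant's best interest may be omitted or deferred.*

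Add to 6.3:

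> *For participants who stop visits but agree to contact, all AEs are collected by telephone to Week 26.*

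The second sentence for 4.3 matters most. It keeps collection going whichever ground is used, including the wider ones on substantial risk and non-compliance. The omit-or-defer clause follows the approach of 8.2.6.3. The prohibitions in 5.6.1 stay as they are.

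The cost is two short additions, with no extra participants and no clinic visits beyond those in Table 1. Telephone collection adds some calls for those who stop attending. The downside is visit or telephone burden for an ill participant, which the omit-or-defer clause limits.
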